1.1, 1.2, 1.3, 5.1, 5.5, 11	
 Updated amendment history for v3 and v4 Modified descriptions of intervention to clarify two different programs and methods of delivery Updated schema to incorporate Week 12 survey SoA updated to incorporate treatment usage and coping strategy questionnaires; cohort builders generalized Inclusion criteria #1 clarified to indicate that chronic pain conditions are not explicitly limited to those listed in tables Fourth recruitment site added (Bendcare) 	General cleaning of protocol, incorporated new questionnaires, fourth recruiting site added

	
 Supplementary ICD-10 code table created to capture additional qualifying conditions identified by study team 	
1.3	
 SOA modified and clarified 	Additional surveys added, SSQ needed to be separated from Week 1
5.5	
 Recruitment procedures modified to allow for recruitment of individuals with valid email that was not in the electronic medical record 	These individuals should be eligible for enrollment.
5.6, 8.3	
 New CRFs added about primary pain Neck pain added as known risk 	Primary complaint may differ from whichever one of many qualifying ICD-10 codes are found during chart review; neck pain added as risk
5.5, 6.4	
 Recruitment procedures modified to allow for recruitment of individuals by phone or email with elimination of 7 day waiting period. Compliance procedures modified to allow for student interns with restricted access to PHI to make calls relating to facilitate survey compliance and device returns. 	
Recruitment efforts to date suggest letters and waiting period are ineffective for this study population; all study teams agree that removing email requirements for contact improves access, equity, and diversity of potential study population.
 
Some basic tasks involving brief interactions with patients to be delegated to student interns when possible.

2.3.1, 10.1.8.1	
 Microsoft OneDrive added as possible secure cloud data management system 	OneDrive has features favorable to study staff that Box cannot accommodate; several study processes

5.5	
 Onboarding procedures modified to take into account new instructional videos Compliance procedures clarified and modified to account for optional SMS text messaging via REDCap 	
Onboarding procedures now incorporate clear video instructions, and compliance monitoring updated to reflect current streamlined practices

6.0	
 Exclusion criteria expanded to include history of seizure and prior exposure to either study intervention Screener week failure criteria modified to exclude if any of 7 pain journals incomplete, housekeeping to reflect contents of finalized screener week surveys and procedures Monitoring procedures expanded to allow for optional onboarding phone call, as instructional materials have for many patients rendered technical support calls obsolete. Patients may now use email confirmation to begin study procedures (see new study document "Study Onboarding Communications") Survey expirations (active and screening) clarified and follow-up procedures modified to provide flexibility to study staff and statisticians Defined expectation of survey missingness 	
Survey procedures modified following findings of 2022 monitoring visit by CS-IRB. Onboarding procedures streamlined to ease patient burden and adjust for changes to call screening for unknown numbers, which may cause participants to be unfairly withdrawn.

5.5, 7.2	
 Included protocol for study staff to contact individuals who have not signed the ICF Modified definition of replaceable participant to exclude individuals who used VR intervention before withdrawing from study 	
Contacting screened participants to possibly assist with eConsent can be used to improve sample diversity and enrollment.
 
Study adequately powered based on withdrawals to date, and analyses should include individuals who found the intervention

		unsatisfactory and subsequently withdrew
5.5	
 • Compliance procedures modified to allow a participant's recruiting site study staff to contact via patient portal when allowed by their local IRB. 	Study team is having difficulty contacting participants at non-CSMC from a California phone.

Abbreviations

AE	Adverse Event
CFR	Code of Federal Regulations
CLBP	Chronic Low Back Pain
CONSORT	Consolidated Standards of Reporting Trials
CBT	Cognitive Behavioral Therapy
CRF	Case Report Form
eCRF	Electronic Case Report Forms
EHR	Electronic Health Record
GLP	Good Laboratory Practices
HIPAA	Health Insurance Portability and Accountability Act
IRB	Institutional Review Board
ITQ	Immersive Tendency Questionnaire
LBP	Lower Back Pain
MRN	Medical Record Number
NCT	National Clinical Trial
NIH	National Institutes of Health
OHRP	Office for Human Research Protections
PI	Principal Investigator
QA	Quality Assurance
QC	Quality Control
SAE	Serious Adverse Event
SAP	Statistical Analysis Plan
SOA	Schedule of Activities
UP	Unanticipated Problem
US	United States
VR	Virtual Reality

1 PROTOCOL SUMMARY

1.1 SYNOPSIS

Title: Transcending COVID-19 barriers to pain care in rural America: Pragmatic comparative effectiveness trial of evidence-based, on-demand, digital behavioral treatments for chronic pain

Study Description: This study will compare two available, evidence-based, digital pain treatment programs that patients can use at home. The goal is to see if one approach is better than the other, and whether certain patients respond to one more than the other. Study participants will be randomized to receive one of two treatment programs: Skills-Based VR or PainTRAINER. Study devices will be delivered to the participant's home with instructions for use via FedEx; participants will receive remote technical support. They will be followed for 8 weeks and complete Patient Reported Outcome (PRO) questionnaires to assess functional status, pain levels, and use of pain medications (including opioids). Participants will also be asked to provide consent/authorization to access medical records from their treating facility.

[figure not shown]
Objectives: Primary Objective:
To compare the effectiveness of EaseVRx and PainTRAINER in improving perceived pain intensity from baseline to 8 weeks.

Secondary Objectives:

- To compare the effectiveness of EaseVRx and PainTRAINER in improving perceived pain catastrophizing over 8 weeks.
- To compare the effectiveness of EaseVRx and PainTRAINER in improving PROMIS anxiety over 8 weeks.
- To compare the effectiveness of EaseVRx and PainTRAINER in improving PROMIS pain interference over 8 weeks.
- To compare the effectiveness of EaseVRx and PainTRAINER in improving pain self-efficacy over 8 weeks.
- To compare the effectiveness of EaseVRx and PainTRAINER in reducing use of opioids over 8 weeks.

Endpoints:	Primary Endpoint: Daily Pain Intensity Secondary Endpoints: PROMIS Pain Interference, PROMIS Anxiety, Pain Catastrophizing, Pain Self-efficacy, and MME usage.
Study Population:	Individuals over age 13 with an ongoing pain problem that have experienced average pain intensity of >3 out of 10 within the previous 7 days.
Phase:	Phase 2
Description of Sites/Facilities Enrolling Participants:	Four outpatient clinic sites, including Cedars-Sinai Medical Center; Ochsner Medical Center; The University of Alabama at Birmingham; Bendcare Physician Network. In addition, participants may enroll remotely.
Description of Study Intervention:	All participants will randomly receive one of two interventions: a VR headset with a 3D Immersive VR therapy (EaseVRx) or a web-based 2D mHealth intervention therapy(PainTRAINER)
Study Duration:	36 months
Participant Duration:	12 weeks

1.2 SCHEMA

1.3 SCHEDULE OF ACTIVITIES (SOA)

Procedures	Baseline / Screening	Day 1 of Week 1	8-Week Intervention									Post Intervention
	0	1	1	2	3	4	5	6	7	8	9	
Week	0	1	1	2	3	4	5	6	7	8	9	12
Prospective patients identified (Cohort Builder or Provider)	X											
Informed consent in person or over phone	X											
Verify eligibility in chart review or from [name]:	X											
• Medical history												
• Demographics												
Randomization	X											
Baseline Questionnaires (Listed below with)	X											
Shipment of VR device and/or study documents	X											
Technical onboarding call		X										
Milligram Morphine Equivalent (MME) Daily Dose	X										X	
Return of VR Device												X
Deliver honorarium						X					X	X
Self-Reported Questionnaires												
NIH developed baseline demographics, biological sex	X (Day 1)											
Daily Pain Medications Used	X										X	
Daily Pain Intensity	X										X	
Pain Catastrophizing Scale	X (Day 4)		X	X	X	X	X	X	X	X	X	
PROMIS Anxiety Scale	X (Day 4)		X	X	X	X	X	X	X	X	X	
PROMIS Pain Interference Scale	X (Day 4)		X	X	X	X	X	X	X	X	X	
The Pain Self-Efficacy Questionnaire (PSEQ) 2-item short form	X (Day 4)		X	X	X	X	X	X	X	X	X	
Simulator Sickness Questionnaire (VR Only)		X										
Treatment Usage Questionnaire			X	X	X	X	X	X	X	X	X	X
Events Assessment			X	X	X	X	X	X	X	X	X	
Custom Questions		X									X	
Treatment Expectation	X (Day 4)	X										
Concomitant Procedures Questionnaire	X (Day 4)										X	
Primary Pain Questionnaire											X	
Coping with Weekly Pain Questionnaire	X (Day 7)										X	X

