2.2 BACKGROUND

The COVID-19 Pandemic Presents Unique Biopsychosocial Barriers to Patients with Chronic Pain

More than 50 million Americans suffer from chronic pain,¹ defined as pain that persists for six months or longer.² In addition to experiencing the physical symptom of pain, patients with chronic pain endure a multi-dimensional illness affecting biopsychosocial health, including low energy, impaired cognitive functioning, disrupted sleep, and diminished physical health, mental health, and social functioning.³⁻⁹ As a result, patients with chronic pain interact with the healthcare system frequently; one in five visits to a primary care provider is related to pain.¹⁰

The COVID-19 pandemic presents unique environmental, social, and physical barriers to patients with chronic pain. Data reveal that the global pandemic can worsen physical pain and trigger anxiety,

depression, insomnia, and substance use.¹¹⁻¹³ This psychological distress is exacerbated by physical and social isolation, fear of seeking in-person visits, and diminished ability to access clinical care.^{11,13}

Although video telemedicine visits are vital to bridge physical gaps between patients and providers, they are insufficient to address the scale of pain-related medical needs and emotional distress created by the pandemic. Video visits and online support groups rely on the availability of a fixed and limited number of trained clinicians. This structural limitation cannot address the overwhelming impact of COVID-19 on mental health, including the 31% of Americans endorsing anxiety and depression during the pandemic, 13% who started or increased substance use, and 11% who seriously considered suicide during this period, according to U.S. Centers for Disease Control data.¹⁴ In addition, telemedicine video visits can only occur at certain times of day and require that patients are willing to participate, are physically available and mentally prepared at the scheduled time, and reside in a home that affords sufficient privacy from others. Thus, additional treatment options are needed to bridge the growing gap between supply and demand of pain care services in the era of COVID-19.¹¹ This need is especially pressing for patients living in rural areas and the socially disadvantaged.

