6.4 STUDY INTERVENTION COMPLIANCE

Data collection will be monitored daily by the study team. Participants will initially be sent automated reminder emails when they have not completed a survey questionnaire within a certain time frame after the original scheduled datetime. For the screener week and Week 8 daily pain journals, these reminders will occur 12 hours after and then 7 days after the original send datetime to best avoid overlapping

responses. For weekly surveys (SSQ+ to Week 8), automated reminder emails will be sent 48-hours after the original send datetime; if the participant does not respond to the first reminder, two additional 48-hr reminders will be sent. Study team members will call the participant after the third reminder if no or incomplete data are received. The participant will be asked why they missed all three reminders and be encouraged to continue to complete surveys as they are sent. If the participant continues to miss subsequent surveys, they will be sent emails containing link(s) to active and incomplete surveys or considered lost to follow-up at the discretion of the study team.

Study participants are not expected to complete 100% of surveys sent to them during the course of the study; incomplete surveys are not considered non-compliance with the protocol. In addition, surveys may be completed out of temporal order and on the same day(s)—study statisticians will determine usability of these data.

Participants who are unable to complete $\geq 80\%$ of surveys sent during any of the three months of follow-up will be ineligible for the corresponding Amazon e-gift codes (\$50 for month 1, \$225 for month 2, and \$25 for month 3, respectively).

Student interns with access only to the names and phone numbers of participants needing contact may place phone calls relating to survey compliance and return of equipment. Interns will **not** be performing activities related to recruitment or consent. If a subject has any questions outside of administrative issues, the call will be immediately transferred to a research coordinator or investigator.

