7.3 LOST TO FOLLOW-UP

A participant will be considered lost to follow-up if he or she fails to schedule an onboarding phone call within 30 days of device delivery or if he or she fails to complete the initial SSQ+ survey within 30 days of onboarding completion. For participants who complete the initial SSQ+ survey and fail to complete >80% of future surveys, and become unreachable by phone or email, the participant will be considered lost to follow-up 6 days following the email date of the participant's Day 60 survey.

If a participant fails to complete the weekly surveys within six days, the following actions will be taken:

- The research coordinator will attempt to contact the participant and counsel them on the importance of completing surveys and returning the equipment to be eligible for the gift card.
- Before a participant is deemed lost to follow-up, the investigator or designee will make every effort to regain contact with the participant (where possible, 3 telephone calls and, if necessary, a certified letter to the participant's last known mailing address or local equivalent methods). Contact attempts will be documented in the participant's study record.
- Should the participant continue to be unreachable, he or she will be considered to have withdrawn from the study with a primary reason of lost to follow-up.

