8.3 ADVERSE EVENTS AND SERIOUS ADVERSE EVENTS

8.3.1 DEFINITION OF ADVERSE EVENTS (AE)

An adverse event (AE) is defined as any untoward medical occurrence associated with the use of an intervention in humans, whether or not considered intervention-related (21 CFR 312.32 (a)). Short-term AEs associated with the study include "cybersickness,"³² a transient form of motion sickness that affects up to one in four people upon entering a VR environment. Cybersickness most commonly presents with a short-term feeling of dizziness that typically subsides quickly. There are no anticipated long-term AEs from participating in this study. A comprehensive list of all potential cybersickness symptoms can be found below:

- Nausea
- Fatigue
- Eyestrain
- Blurred vision
- Difficulty focusing
- Dizziness
- Vertigo (a sensation of spinning dizziness, as though the room or surrounding environment is spinning)
- Headache
- Fullness of the head
- Difficulty concentrating
- Postural instability

In very rare instances, materials used in VR headsets have caused a mild rash which resolves when the VR headset is discontinued. Participants may also experience neck pain if using the device. No AEs are expected with PainTRAINER.

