8.3.3 CLASSIFICATION OF AN ADVERSE EVENT

8.3.3.1 SEVERITY OF EVENT

For adverse events (AEs) the following guidelines will be used to describe severity.

- **Mild** – Events require minimal or no treatment and do not interfere with the participant's daily activities.
- **Moderate** – Events result in a low level of inconvenience or concern with the therapeutic measures. Moderate events may cause some interference with functioning.
- **Severe** – Events interrupt a participant's usual daily activity and may require systemic drug therapy or other treatment. Severe events are usually potentially life-threatening or incapacitating. Of note, the term "severe" does not necessarily equate to "serious".

Research staff will call the patient if an event is noted in event assessment that is sent on a biweekly basis. Nothing more than mild to moderate side effects are expected.

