8.3.4 TIME PERIOD AND FREQUENCY FOR EVENT ASSESSMENT AND FOLLOW-UP

The occurrence of an adverse event (AE) or serious adverse event (SAE) may come to the attention of study personnel during review of biweekly event assessments by a study team member as well as on

Day 1. We will employ a general question to allow the patient to provide an event description without bias by presupposing the nature of the event, as follows:

- 1) During the past 14 days, have you experienced anything uncomfortable, distressing or upsetting as a result of using the technology?
 - a. Yes
 - b. No
- 2) If Yes please describe what happened. A research staff member will follow-up with you as soon as possible to learn more.
 - a. [open text]

A designated CRC will review the REDCap dashboard for completed AE assessments on a daily basis throughout the work week. Once they find a completed event assessment form, they will follow-up with a phone call. The following information be obtained from the patient during the call: onset of potential adverse event, event description, when they last used the technology, how long they used the headset, when they stopped using the headset, severity of the potential AE, outcome of the potential AE (see categories, below), time until resolution/stabilization of event, the perceived relationship of the event to the study intervention, whether or not the event was expected (Y/N), whether it was serious.

The outcome can be labeled using one of the following categories:

- Recovered, without treatment
- Recovered, with treatment
- Still Present, no treatment
- Still Present, being treated
- Residual effect(s) present-no treatment
- Residual effect(s) present-being treated

Research staff will record all reportable events with start dates occurring any time after informed consent is obtained until 7 (for non-serious AEs) or 30 days (for SAEs) after the last day of study participation.

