• tension headache • tension type headache • stress headache • tension-vascular headache	G44.209	2873	2835, 98.6%		
	G44.211	42	42, 100%		
	G44.219	809	808, 99.9%		
	G44.221	447	446, 99.8%		
	G44.229	1274	1272, 99.8%		

COPC/Search terms	ICD-10 Code	N with code	N captured by search terms, %	True Positive, %	False Negative, %
Temporomandibular disorder	M26.60	1293	1265, 97.8%	18/20, 90%	9/20, 45%
• temporomandibular disorder • TMD • temporomandibular joint disorder • TMJD • temporomandibular joint disease • (“temporomandibular” AND (“disease” OR “disorder”)) • TMJ syndrome • TMJ arthralgia • TMJ tenderness • TMJ pain • TMJ disease • TMJ dysfunction • temporomandibular joint syndrome	M26.62	1474	1462, 99.9%		
	M26.63	616	614, 99.7%		
	S03.0XXA	326	293, 89.8%		
Chronic low back pain	M54.5	43,850	33,169, 75.6%	19/20, 95%	8/20, 40%
• back pain chronic~6 • back pain persistent~6 • back pain recurrent~6 • back pain unspecified~6 • back pain nonspecific~6 • back pain idiopathic~6 • back pain functional~6	M54.40, 41, 42	10649	9470, 88.9%		
	M54.89	804	644, 80.1%		
Chronic fatigue syndrome	R53.82	8917	8916, 99.9%	20/20, 100%	0/1, 0%
• chronic fatigue • chronic fatigue syndrome • myalgic encephalomyelitis • CFS • ME/CFS • systemic exertion intolerance disease • SEID					
Endometriosis With pain	N80.XXX AND	1586	1561, 98.4%	18/20, 90%	6/20, 30%
• endometriosis pain~4 • endometriosis painful~4 • endometrioma pain~4 • endometrioma painful~4 • adenomyosis pain~4 • adenomyosis painful~4 • (“endometriosis” OR “endometrioma” OR “adenomyosis”) AND (“pelvic pain” OR “dysmenorrhea” OR “dyspareunia” OR “intercourse pain”~4 OR “intercourse painful”~4))	(“R10.2” OR “N94.4” OR “N94.5” OR “N94.6” OR “N94.10” OR “N94.11” OR “N94.12” OR “N94.19”)				

Table 3.

Additional codes identified by study team which capture chronic pain conditions.

ICD-10 Code	Description
M05.*	Rheumatology
M06.*	
M45.*	
M46.*	
L40.5*	
M1A.*	
M15.*	
M16.*	
M17.*

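### The Simulator Sickness Questionnaire is collected once, in the VR arm only and with no pre-exposure score, so its results could be misattributed to VR; separately, the event form's interval and recall period conflict.

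*Combined protocol and SAP*

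**What the plan says.** **Simulator sickness.** The Schedule of Activities lists "Simulator Sickness Questionnaire (VR Only" with one mark, in the column for Day 1 of Week 1. Nothing is marked at Baseline/Screening, in the later weeks or at Week 12. Section 7.3 places the survey that carries it after onboarding: a participant is lost to follow-up who "fails to complete the initial SSQ+ survey within 30 days of onboarding completion". Section 6.4 treats the same survey as the first of the weekly series, with no restriction by arm: "For weekly surveys (SSQ+ to Week 8), automated reminder emails will be sent 48-hours after the original send datetime".

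**Symptoms and population.** Section 8.3.1 states "A comprehensive list of all potential cybersickness symptoms can be found below". The list includes headache, fatigue, nausea, dizziness, difficulty focusing and difficulty concentrating. Table 2, after the references, gives qualifying diagnoses that include migraine, chronic tension-type headache and "Chronic fatigue syndrome". Section 2.2 describes chronic pain as "including low energy, impaired cognitive functioning, disrupted sleep" among other effects. The examples in the section 5.2 exclusions name none of these conditions.

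**Event form.** The Schedule marks the Events Assessment every week from Week 1 to Week 9. Section 8.3.3.1 refers to an "event assessment that is sent on a biweekly basis", and the item in section 8.3.4 reads "During the past 14 days, have you experienced anything uncomfortable, distressing or upsetting as a result of using the technology". Section 10.1.2 also refers to assessments at 14-day intervals.

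**The concern.** A symptom score taken once, in one arm, supports neither a change within the participant nor a contrast between arms. In a population where headache, fatigue and poor concentration are common reasons for being a patient, such a score mixes the condition with the device.

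Cybersickness is the main harm the protocol names for VR. Section 2.3.2 presents the trial as a source of knowledge on the safety of therapeutic VR. Section 8.2 makes questionnaires part of safety monitoring, and section 9.3 says safety summaries will be given by study arm. A VR-only reading cannot supply that comparison, and nothing in the plan stops a raw score from being read as sickness caused by VR.

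The event form raises a separate question. If it goes out weekly but asks about 14 days, the same event can be reported on two forms.

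**Working it through.** The plan gives no figure for this point, so there is nothing to reproduce. The check is an illustration of size and a count of recall windows.

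**Inputs**
- t, the proportion with VR-induced symptoms: 25%, the upper figure in section 8.3.1 (at most one person in four). The protocol does not say whether that figure is net of background symptoms.
- b, the proportion who would report a listed symptom on that day without VR: not in the documents. Assumed 10% to 50%.
- VR arm size: 150 (section 9.2).
- Also assumed: background and VR-induced symptoms are independent, and a participant counts as positive with any listed symptom. The plan states no such counting rule.

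**Formulas**
- Observed prevalence = 1 − (1 − t)(1 − b).
- Excess over the true rate = observed − t = b(1 − t).

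Example: b = 10% gives 1 − 0.75 × 0.90 = 0.325, and the excess is 0.325 − 0.25 = 0.075, or 0.075 × 150 = 11.25 participants.

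| b (assumed) | Observed, t = 25% | Excess, points | Excess among 150 | Share of positives not due to VR |
|---|---|---|---|---|
| 10% | 32.5% | 7.5 | 11.3 | 23% |
| 20% | 40.0% | 15.0 | 22.5 | 38% |
| 30% | 47.5% | 22.5 | 33.8 | 47% |
| 50% | 62.5% | 37.5 | 56.3 | 60% |

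A smaller true rate makes the excess larger. With t = 5%, also an assumption, observed prevalence is 14.5% at b = 10% and 52.5% at b = 50%, an excess of 9.5 to 47.5 points.

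**What a comparator score would add.** With the questionnaire in both arms, the difference is t(1 − b): 22.5, 20.0, 17.5 and 12.5 points for the four rows above. Dividing by (1 − b), which the PainTRAINER arm estimates, returns t: 0.225 / 0.90 = 0.25 and 0.125 / 0.50 = 0.25. A baseline score alone recovers t among participants who were symptom-free, provided background symptoms are stable. Where they fluctuate from day to day, the comparator arm is needed as well.

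**Recall windows.** Take nine weekly forms completed on schedule, each covering the previous 14 days. An event in the week before form k is covered by form k and by form k + 1. Only the week before form 9 has no later form. Eight of the nine weekly intervals are therefore covered twice and one is covered once. With a form every 14 days, each event would fall in one window.

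**The case against.** The strongest reply is that the plan never uses the questionnaire in the way that would cause the error. It is not a primary, secondary or exploratory outcome. No section gives it a score, a cut-off or a definition of VR intolerance, and section 9.4.4 makes safety purely descriptive. Adverse events come by another route: an item about discomfort resulting from the technology, not limited to the VR arm, then a staff call that records onset, last use, duration of use and perceived relationship. Section 8.3.3.2 allows an event to be classed as unrelated where another cause is established.

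This stands against the stronger reading that existing headache and fatigue will be counted as VR intolerance. A reader might infer that, but the documents contain no rule that does it. The reply does not remove the point. Section 8.3.3.2 also lets an event be classed as related because it is known to occur with the intervention or follows it in time, and there is no pre-exposure score to help establish another cause. Section 8.3.4 says events may come to light on Day 1, yet the Schedule has no Events Assessment that day; its only symptom questionnaire then is the VR-only one.

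Three further objections hold in part:
- That the questionnaire follows the first VR session is inferred from its Day 1 position and from its place after onboarding; it is not stated. If it comes before first use, it measures no VR effect at all. Either way the timing needs stating.
- A reader might infer that every event is counted twice. Events in the last week fall in one window, and the onset date taken at the call allows duplicates to be recognised. Duplicate forms are not duplicate events. The plan states no rule for removing them, however.
- The trial is well under way (version 6.2 is dated 10/17/23), so a new baseline would cover only later enrolees.

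**Conclusion.** The point holds as a limit on interpretation. A single VR-only score cannot separate existing symptoms from device effects, and its results could be misattributed to VR if reported as VR-induced sickness. It is not a demonstrated bias in a planned result, because the plan specifies no such report.

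The direction of any error would be upward; its size is unknown. At the protocol's 25% and an assumed, independent background of 10% to 50%, the overstatement would be 7.5 to 37.5 points, or about 11 to 56 of 150 VR participants. Those figures depend on the assumed background, on independence and on counting any listed symptom. The primary and secondary efficacy analyses are unaffected.

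The event-form conflict is a separate inconsistency, and it is plain on the page: weekly in the Schedule, biweekly with 14-day recall in sections 8.3.3.1 and 8.3.4. As written, most events fall in two recall windows.

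**What to change.** **Questionnaire, remaining enrolees.** Add the existing form to a Screening Week survey (Day 4 or Day 7) and to the Day 1 survey in both arms. State whether the Day 1 form follows the first VR session. Report change from baseline, and new or worsened symptoms, by arm.

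**Questionnaire, participants without a baseline.** Report scores by baseline headache or fatigue diagnosis, using the medical history and pain condition already collected. Label them as symptom levels, not as VR-induced incidence.

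**Event form.** Reconcile the Schedule with sections 8.3.3.1 and 8.3.4 so that the recall period equals the interval between forms. De-duplicate reports already collected by the onset date recorded at the follow-up call, and write that rule down.

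**Cost.** An existing REDCap form added to two existing surveys, a few minutes of participants' time, and changes to the Schedule and analysis text. The questionnaire data will be mixed, with a baseline for later enrolees only.
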